We have demonstrated, in rodents (Chierichetti, 2012), and in a large animal [i.e. anesthetized pig with lung injury] model (Yoshida, 2017) that CNAP augments oxygenation and improves compliance, and importantly, it reduces the degree of subsequent lung injury. In the rodent application, the animals developed hypotension, but not in the large animal model. We have recently completed a Phase 1 study on healthy volunteers (HSC REB#1000057680). This demonstrated that the CNAP is well tolerated in awake healthy subjects and caused no adverse effects. Others have used a variation of this approach in anesthetized pigs (Valenza, 2005) and in humans with ARDS (Valenza, 2003), but they did not use recruitment maneuvers; and, the devices used did not encircle the abdomen or achieve effective transmission of negative pressure across the abdominal wall.

In these applications, the approach did not augment ventilation but, neither did they cause any adverse impact.

Finally, the technique has been used (although for a different indication) to reduce elevated intra-abdominal pressure in critically ill patients (Bloomfield, 1999 #247).

Device: A patent (US) application has been filed for the device (owned by SickKids)

RESEARCH OBJECTIVES AND HYPOTHESIS

We wish to perform a safety, 'Phase 2' study in patients that have been diagnosed with Acute Respiratory Distress Syndrome (ARDS) to determine primary safety and efficacy of using CNAP.

Safety (Stop rules)

↓mean arterial pressure <60 mmHg or ↓15%
(despite 500 mL fluid or increase norepinephrine)
↓SpO2 (drop >5%)
↓PaO2/FiO2 >20% .

Efficacy ↑PaO2/FiO2 >20%

RECRUITMENT PROCESS

Patients will be recruited from the Intensive Care Unit, following completion of informed consent from the patient or legally authorized substitute decision maker (SDM) (see Consent Form). Please see "Inclusion and Exclusion criteria"

POPULATION TO BE STUDIED

Patients with ARDS. Weight range 40-100 kg. Ventilated with positive pressure ventilation and a P/F ratio ≤200 mmHg with PEEP ≥5 cmH2O

Inclusion Criteria:

- 1) Patients ≥ 18 years old
- 2) Patients with moderate to severe ARDS as per the Berlin definition (PaO2/FiO2 ≤200mmHg) (Ranieri, 2012)
- 3) Patients with absence of any significant cardiopulmonary disease

Exclusion Criteria:

- 1) Contraindication to CNAP
 - a. open abdominal wounds or drainage tubes
 - b. Acute brain Injury with intracranial pressure >30 mm Hg or cerebral perfusion pressure <60 mmHg

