the suction level will be increased until esophageal pressure will decrease by -3cmH₂O, as per the primary team, and vital signs recorded. If no impact, go to next stage after discuss with the clinical team and attending physician responsible for the patient's care

9) Stage 4 & 5

First, lung recruitment with CPAP 40cmH₂O for 10sec. Then the suction will be applied until esophageal pressure will decrease by -3cmH₂O, as per the primary team, and vital signs recorded.

10) Stage 6

when the study is finished, and the device removed, monitoring will continue –along with primary team- as per usual ICU care.

At each stage, if any concern (Safety-Stop rules, see above), the primary care team will immediately stop the CNAP. If effective (Efficacy, see above), CNAP will continue for 2 hours.

If the device appears to have helped, it can (at the request of the care team) be left in place for a total of 24h.

A SCHEMATIC of the study protocol is appended (Flow chart).

The following parameters will be recorded (see Flowchart & Case report form).:

Hemodynamic (S/M/DAP, HR, CVP)

Respiratory Mechanics (RR, VT, mPaw, PIP, Pplat, PEEP, end-exp. Pes, EIT)

Gas Exchange (FiO₂, SpO₂, PaO₂, PaCO₂)

Abdominal Pressure (Pbladder)

ANTICIPATED OUTCOME

We anticipate no significant impact on cardiovascular physiology; we expect some improvement of the P/F ratio, lung compliance and ventilation distribution.

SAMPLE SIZE AND JUSTIFICATION

A convenience sample size of 20 patients will be invited to participate. We anticipate that patient oxygenation will increase with CNAP application in conjunction with positive pressure ventilation vs positive pressure ventilation alone.

Because we will use sensitive markers of any impact on respiratory or circulator parameters (including patient reported dyspnea, and key parameters (see Data Sheet), this will facilitate detection of any potentially adverse effects.

RESEARCH PROCEDURES

Analysis will consist of inspection of the data associating transition to and withdrawal from CNAP.

We estimate that the total time in the CNAP device might be around 6 hours, but it could take less time or more time. Throughout this period, close monitoring will ensure comfort and safety.

SAFETY PROCEDURES

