- 1) Transpulmonary pressure (PL): Maximal values of PL = [airway pressure – esophageal pressure] will be recorded as peak PL. We also will calculate Δ PL as the difference between the airway driving pressure and Δ esophageal pressure (i.e. airway pressure – PEEP – Δ esophageal pressure) corresponding to the same time phase and we will pick up the maximal value as peak Δ PL. Plateau PL will be calculated as [airway pressure - esophageal pressure] after making an inspiratory hold (i.e. zero flow phase). Expiratory PL will be calculated as [airway pressure - esophageal pressure] after making an expiratory hold.
- 2) Airway pressure and flow: Plateau pressure, peak airway pressure and PEEP will be measured, as previously described (Henderson, 2017). Tidal volume will be calculated as integral of flow. Considering the total stretching pressure across respiratory system (lung + chest wall) with spontaneous breathing during mechanical ventilation, driving pressure will be calculated as the sum of [plateau pressure – PEEP] and the changes in esophageal pressure corresponding to plateau phase when compared with passive conditions (Yoshida, 2013). During muscle paralysis, driving pressure was calculated as [plateau pressure – PEEP]. The dynamic compliance of the respiratory system was defined as: [VT/ driving pressure].

Hemodynamics: Arterial blood pressure and heart rate will be continuously monitored on the ICU bedside monitor.

Arterial Blood Gas: pH, PaCO₂, PaO₂ will be measured by standard clinical technique using the ICU blood gas analyzer.

STATISTICAL ANALYSIS

Statistical analysis will be performed using standard software SPSS13.0 for Windows (SPSS, Chicago, IL, USA). The results are expressed as mean \pm standard deviation. 1-way analysis of variance for repeated measures will be used to evaluate the impact of time. In the post hoc analysis to separate differences between the means, a Tukey's pair-wise multiple comparison test will be used. All tests were two-tailed, and differences were considered significant when $p < 0.05$

REFERENCES

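### The >20% PaO2/FiO2 efficacy criterion is not carried into the statistical analysis, so no planned result shows whether it was met

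*Combined protocol and SAP*

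**What the plan says.** Under Research Objectives and Hypothesis, the combined protocol and SAP gives one efficacy criterion: "Efficacy ↑PaO2/FiO2 >20"%. The section on interventions uses it for the individual patient at each stage: "If effective (Efficacy, see above), CNAP will continue for 2 hours".

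The inferential plan is in Statistical Analysis: "1-way analysis of variance for repeated measures will be used to evaluate the impact of time", and for the post hoc comparisons "a Tukey's pair-wise multiple comparison test will be used". "All tests were two-tailed", and "differences were considered significant when" p < 0.05. On presentation, "The results are expressed as mean" and standard deviation. That section does not name PaO2/FiO2 as the analysed variable. It does not say whether values are analysed in mmHg, as percentage change or on a log scale, and it does not mention the 20% criterion.

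Research Procedures adds that the data around the start and withdrawal of CNAP will be inspected. On sample size: "A convenience sample size of 20 patients will be invited to participate". No power, target effect, mean baseline PaO2/FiO2 or SD of change is given.

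**The concern.** The objective is framed as a relative change within a patient, with a stated size. The analysis asks only whether stage means differ at all. Nothing planned estimates the percentage change, gives its precision, counts the patients who passed 20%, or sets any result against 20%. The mean and SD at each stage describe the spread between patients. They do not give the precision of the within-patient change, which is what the criterion is about.

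In a single-arm convenience sample of 20, the useful product is an estimate of how large the effect is and how many patients had it. If the plan is followed as written, the report could give a p-value for oxygenation and still leave open whether the protocol's own efficacy criterion was reached. A significant rise well short of 20% and a non-significant rise above 20% are both possible, and the planned output would not explain either.

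**Working it through.** The plan states no effect size, SD or power, so there is no figure of its own to reproduce. The check is how large an observed rise must be before the planned test calls it significant, compared with 20%.

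**Inputs from the document**
- n = 20, two-sided α = 0.05, Tukey pairwise comparisons after a one-way repeated-measures ANOVA.
- Efficacy threshold: ratio 1.20, so ln(1.20) = 0.1823.

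**Assumptions, because the document is silent**
- k = 6 repeated stages as the main case. The protocol describes a baseline and Stages 1 to 6 without saying which enter the ANOVA, so k = 5 and k = 7 are also shown.
- SD of the within-patient log change, s, from 0.15 to 0.40.
- Log scale for this calculation, sphericity, and all 20 patients measured at every stage.

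**Formula.** With mean square error s²/2, the smallest significant difference is q(0.05; k, (k−1)(n−1)) × s / √(2n). For k = 6 the error degrees of freedom are 5 × 19 = 95 and q = 4.114, so the multiplier is 4.114/√40 = 0.650. For k = 5 it is 0.625 and for k = 7 it is 0.671.

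**Smallest significant rise, k = 6**

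| SD of log change | exp(0.650 × s) | Rise needed |
|---|---|---|
| 0.15 | 1.102 | 10% |
| 0.20 | 1.139 | 14% |
| 0.28 | 1.200 | 20% |
| 0.30 | 1.215 | 21.5% |
| 0.40 | 1.297 | 30% |

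The crossover, where significance and the threshold coincide, is s = 0.1823/0.650 = 0.28. It is 0.29 for k = 5 and 0.27 for k = 7, so the choice of k matters little.

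**Same check in mmHg.** The multiplier now applies to the SD of the raw change. At an assumed baseline of 150 mmHg, 20% is 30 mmHg. SDs of 10, 30, 50 and 60 mmHg need mean rises of 6.5, 19.5, 32.5 and 39.0 mmHg, which are 22%, 65%, 108% and 130% of the threshold. The crossover is at an SD of 0.20/0.650 = 31% of baseline, or about 46 mmHg.

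**What just-significant means for patients.** If percentage changes are roughly normal with an SD of 15 points, the smallest significant mean rise is 0.650 × 15 = 9.8%. The share of patients above 20% is then 1 − Φ((20 − 9.8)/15) = 1 − Φ(0.68), or about 25%.

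**What a direct count would show.** With 20 patients, exact 95% CIs for the proportion with a rise above 20% are 27% to 73% for 10/20 and 51% to 91% for 15/20.

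**The case against.** The best defence is that the 20% is a bedside rule for continuing CNAP, not an endpoint. The plan never says that p < 0.05 establishes efficacy. Its stated expectation for the group is directional: some improvement in oxygenation. A test against no difference fits that expectation, and a significant rise below 20% is still a rise.

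Part of this stands. A reader might infer that the plan would declare efficacy on a significant ANOVA; the document does not say so. But the 20% also appears under the objectives as the only definition of efficacy. If it is purely a bedside rule, the efficacy objective has no group-level definition at all.

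Two other stronger readings are tempting and should not be made:
- That significance arrives at about half the threshold. This follows only if the SD of change is near 0.15 on the log scale. The plan gives no SD, and above about 0.28 the direction reverses.
- That the analysis is in mmHg and so gives less sick patients more weight. The plan does not name the scale, and an ANOVA of percentage change or log values would also fit its text. The sound criticism is that the variable and scale are unspecified, not that the wrong scale was chosen.

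**Conclusion.** The concern holds as a missing link between objective and analysis, and it is worth a cheap correction. That the 20% criterion enters no planned estimate, test or count follows from the document alone.

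The size of the mismatch is conditional. Under the assumptions above, Tukey significance needs a rise of only about 10% to 14% at a log-change SD of 0.15 to 0.20, and more than 20% once the SD exceeds about 0.28. Patients stopped under the safety rules would lack later stages, which would leave fewer than 20 complete cases and raise these minimum rises. The conclusion that significance and the criterion can part company, in either direction, does not depend on which SD is true.

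**What to change.** Keep the ANOVA and Tukey tests, name PaO2/FiO2 as an analysed variable, and state its scale. Then add two summaries for PaO2/FiO2:

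1. The within-patient ratio (or percentage change) of the CNAP stage to the no-suction reference, with a 95% CI, stated against both no change (1.00) and the plan's own 1.20. Stage 1, with the device on but no suction, is the natural reference. The CNAP stage to be used should be named in advance.
2. The number and proportion of patients with a rise above 20%, with an exact 95% CI.

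Describe a significant rise whose estimate is below 20% as a rise below the planned threshold. Do not add a pass/fail rule that the group estimate must reach 1.20. That would turn a per-patient criterion into a group one, and it would fail about half the time when the true rise is exactly 20%. The bedside continuation and stop rules are not affected.

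The cost is a few lines of SAP text and slightly more analysis, with no new data or patients. The downside for the sponsor is that a small significant rise can no longer be presented as meeting the efficacy criterion.

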 - c. Decompensated heart insufficiency or acute coronary syndrome
 - d. Major hemodynamic instability: Mean arterial pressure lower than 60 mm Hg despite adequate fluid resuscitation and two vasopressors or increase of vasopressor dose by 30% in the next 6 hours.
 - f. Unstable spine, femur, or pelvic fractures
 - g. Pregnancy
 - h. Pneumothorax
- 2) Contraindication to EIT electrode placement
Burns, chest wall bandaging limiting electrode placement
- 3) Severe liver insufficiency (Child-Pugh score > 7) or fulminant hepatic failure
- 4) Major respiratory acidosis or PaCO₂ > 60 mmHg
- 5) Severe COPD (according to the GOLD criteria defined as severe = FEV1: 30-50% or very severe = FEV1 < 30%)
- 6) Clinical judgement of the attending physician

INTERVENTIONS AND RESEARCH PROCESS

Pre-Human Testing: The device has been extensively tested (the first prototype was successfully tested on a pig with good success (Yoshida, 2017).

The current device has undergone a closed loop stress test for 24 hours (-10 cmH₂O) and showed no signs of failure. This device was made in the laboratory of [name] in the department of Biomedical Engineering.

The device has also been tested on a Mannequin (please see photograph in the appendix), with no leakage.

Protocol (summarized in Flow Chart):

- 1) Eligible patients will be identified with research coordinators by daily screening in the intensive care unit
- 2) Consent for participation will be obtained from the patient's substitute decision maker
- 3) Prior to starting the application of CNAP, patients will be sedated deeply with sedatives and/or opioids, and will be paralyzed with a continuous infusion of rocuronium, if not started (7 µg/kg/min).
- 4) Also we will install the EIT to visualize the ventilation pattern.
- 5) Baseline measurement (see Appendix, ARDS Registry Form)

- a) Lung Mechanics
- b) Pressure-Volume Curve,
- c) determination of Recruitability, and
- d) Fluid Responsiveness.

6) Stage 1

the CNAP device is attached to the abdomen (but no suction), and a complete set of vital signs recorded.

7) Stage 2

a suction is applied to the CNAP device until chamber pressure will reach -5cmH₂O, and vital signs carefully monitored. If no impact, go to stage 3.

8) Stage 3

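### The overall F test has no stated sphericity correction, and the all-pairs Tukey tests name no contrast for the CNAP-versus-ventilation-alone question

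*Combined protocol and SAP*

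**What the plan says.** The Statistical Analysis section gives the overall test as "1-way analysis of variance for repeated measures will be used to evaluate the impact of time", followed by "In the post hoc analysis to separate differences between the means, a Tukey's pair-wise multiple comparison test will be used". Tests are two-tailed at p<0.05. The section does not mention sphericity, list the time levels, state the error term for Tukey, name a primary variable or contrast, or say how patients with missing stages enter the analysis.

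The question itself appears elsewhere. Sample Size and Justification says: "We anticipate that patient oxygenation will increase with CNAP application in conjunction with positive pressure ventilation vs positive pressure ventilation alone". Research Procedures says: "Analysis will consist of inspection of the data associating transition to and withdrawal from CNAP". Neither is tied to a pair of stages or to a test.

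Interventions and Research Process describes a baseline measurement and six stages. At Stage 1 "the CNAP device is attached to the abdomen (but no suction), and a complete set of vital signs recorded". Stage 2 applies a fixed chamber pressure. Stage 3 titrates suction to the individual patient's esophageal pressure, and Stages 4 and 5, described together, add a recruitment step. Stage 6 follows device removal. Progression is conditional: at Stage 2, "If no impact, go to stage 3", and more generally "At each stage, if any concern (Safety-Stop rules, see above), the primary care team will immediately stop the CNAP". Research Objectives and Hypothesis sets a per-patient response threshold, "Efficacy ↑PaO2/FiO2 >20" per cent.

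**The concern.** There are two separate issues.

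**Validity.** The uncorrected repeated-measures F test is exact only under sphericity, that is, when differences between any two stages have the same variance across patients. Conventional Tukey tests after this ANOVA divide every pair by one pooled error and rest on the same condition. This design could break it. Stages without suction should differ from each other mainly by reading noise, while stages with individually titrated suction also carry each patient's own response. The pooled error would then be too small for late-stage contrasts and too large for early ones.

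**Targeting.** A test across time followed by every pairwise comparison does not answer whether CNAP improves on ventilation alone. It spends the error rate on many pairs nobody asked about, and it leaves open which pair will be reported as the result.

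At stake is the reported evidence on oxygenation and arterial pressure. The stop and efficacy rules are per-patient thresholds and do not use these p-values.

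**Working it through.** **Inputs from the documents.** n=20 (a convenience sample, with no power statement to reproduce); two-sided 0.05; Baseline plus Stages 1-6. The levels entering the ANOVA are not stated, so 6 or 7 are used: 6×5/2 = 15 pairs or 7×6/2 = 21 pairs.

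**Assumptions.** Complete data; independent reading error with SD 1; a patient-level response with SD r (the ratio of response SD to reading SD), multiplied by stage weights 0, 0, 0.5, 0.8, 1, 1, 0 for Baseline and Stages 1-6. The documents give no value for r, so a range is shown.

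**Departure from sphericity.** The squared deviations of the weights about their mean sum to 1.334. The population epsilon at 7 levels is (6 + 1.334r²)² / {6[5 + (1 + 1.334r²)²]}. At r=2 this is 11.34² / (6 × 45.2) = 0.47.

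**Pooled against true standard error.** The pooled variance of a difference is 2(1 + 1.334r²/6). The true variance is 2 + r² for Stage 5 minus Baseline and 2 + 0.25r² for Stage 2 minus Baseline. At r=2 the pooled value is 3.78, against 6 and 3, so the SE ratios are √(3.78/6) = 0.79 and √(3.78/3) = 1.12.

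**Error rates.** Simulation with no true mean change, 7 levels, 100,000 trials per setting:

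| r | 0 | 0.5 | 1 | 2 | 4 |
|---|---|---|---|---|---|
| Epsilon | 1.00 | 0.99 | 0.86 | 0.47 | 0.25 |
| Uncorrected F | 5.0% | 5.1% | 5.8% | 9.2% | 13.3% |
| Greenhouse-Geisser F | 3.2% | 3.3% | 3.6% | 4.7% | 5.2% |
| Tukey, any pair | 5.1% | 5.1% | 5.4% | 7.1% | 8.2% |
| Pooled/true SE, Stage 5 minus Baseline | 1.00 | 0.97 | 0.90 | 0.79 | 0.71 |
| Pooled/true SE, Stage 2 minus Baseline | 1.00 | 1.01 | 1.04 | 1.12 | 1.23 |

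At r=0 the nominal 5% is recovered for F and Tukey, which calibrates the simulation. A single paired test stays at 4.9-5.1% throughout.

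**Sensitivity to the pattern.**
- Six levels, r = 1, 2, 4: F 5.6%, 8.6%, 12.2%; Tukey 5.3%, 7.1%, 8.6%.
- Responses correlated only 0.5 across stages, 7 levels, r = 1, 2, 4: F 5.3%, 7.0%, 8.6%; Tukey 5.3%, 6.6%, 7.6%.
- Equal response in Stages 2-5, r = 1, 2, 4: F 6.1%, 10.2%, 13.7%; Tukey 5.3%, 6.6%, 6.5%.
- Extra variability in one stage only, 7 levels, r = 2, 3: F 7.7%, 10.3%; Tukey 8.9%, 11.8%.

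**What r might be for P/F.** Assume half the patients gain 20% and half gain nothing. The response SD is then 10% of P/F, or 10-20 mmHg at P/F 100-200. Ratios of 1, 2 and 4 would need reading SDs of 10-20, 5-10 and 2.5-5 mmHg. The documents do not say which applies.

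**Cost of testing every pair.** The Tukey critical t is q/√2: 4.245/1.414 = 3.00 for 7 levels (df 114) and 4.114/1.414 = 2.91 for 6 (df 95). One paired test needs 2.09 (df 19). For a raw shift of 0.707 reading SD under sphericity, the noncentrality is (0.707/√2) × √20 = 2.24, which gives power of about 23% by Tukey (7 levels) and 56% by one paired test.

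As r grows, the gain shrinks for late stages. Stage 5 minus Baseline at r = 1, 2, 4 has power 19%, 15%, 10% by Tukey and 41%, 23%, 11% by the paired test. Stage 2 minus Baseline has 16%, 7%, 2% and 52%, 41%, 23%.

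**The case against.** The strongest reply is that no error has been demonstrated. The ratio, the stage weights, the number of levels and the completeness of the data are all assumed. Up to a ratio of 1 both tests are close to nominal. The plan does not say that Tukey uses a pooled error; that is the conventional reading. The study is a 20-patient convenience sample whose analysis is partly described as inspection, and the flow chart and case report form, which may list measurement times, are not in the text. All of this stands, and it limits the weight of the point.

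Three stronger readings are tempting and are not supported:

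- **That error rates hold only if responses vary no more than reading noise.** The condition is sphericity, and the ratio matters only together with the pattern. With responses correlated 0.5 across stages, F is 7.0% even at ratio 2. In the other direction, if responses accumulate stage by stage with each increment's SD equal to the noise SD, F is already 7.6%.
- **That the Tukey results are badly inflated.** In most patterns the rate for any pair is about 6-8%; about 9-12% arises only when the extra variability sits in a single stage. The Stage 5 minus Baseline pair alone errs 0.4-4.1% of the time (7 levels).
- **That Tukey must give way to a Holm family.** With three Holm contrasts, late-stage first-step power is 12% and 5% at ratios 2 and 4, below Tukey's 15% and 10%, although Tukey's advantage there comes with inflated family-wise error. That trade-off is optional.

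Nor was the error rate under the actual stop and progression rules computed; the figures assume that all 20 patients supply every stage.

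**Conclusion.** The point holds at modest strength. The omissions are in the text: no sphericity correction, and no contrast tied to the question the protocol asks. The inflation is conditional. The uncorrected F is near 5-6% when response SD is at or below reading SD and about 9-13% at 2 to 4 times it, if each patient's response is shared across stages; it is less if responses correlate weakly. Tukey, read conventionally, is affected less.

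The targeting issue does not depend on unequal variances. The higher critical value applies at every ratio, and the loss of power is plain even under exact sphericity. The gain from one named contrast narrows to almost nothing for late stages at ratio 4.

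Severity is between minor and should-fix: the reported evidence can be made sounder cheaply, but no decision in the documents depends on these p-values.

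**What to change.** 1. Apply the Greenhouse-Geisser correction to any overall F test, and list the time levels that enter it.
2. Pre-specify one primary paired contrast each for P/F and mean arterial pressure: a named CNAP suction stage minus the pre-suction reference at which that variable is measured, with its own SE and 95% CI. For P/F the reference is Baseline unless blood gases are taken at Stage 1, where the text promises only vital signs. For pressure it may be Stage 1 or Baseline. If the named stage is 4 or 5, say which measurement is meant. Label all other pairs, by Tukey or otherwise, as secondary, including withdrawal (Stage 6 minus the last suction stage) if those data are collected.
3. Report the number of patients in each contrast and why the others did not reach that stage.

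**Cost.** SAP wording only, if a pre-suction blood gas is already scheduled, which cannot be confirmed from the text. Greenhouse-Geisser is slightly conservative under sphericity (about 3%). Contrasts not named lose primary status. A paired contrast does not remove selection if progression depends on response, which is why item 3 is needed.
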